9.2 Sample Size Determination

A total of 80 participants are expected to enroll and be randomized in a 1:1 fashion to one of two study arms. Sample sizes are determined by desire to estimate safety and to provide a preliminary idea of efficacy. Given patients will be hospitalized at enrollment, we expect very low missing data rates for early safety and efficacy endpoints. We also expect to be able to have good follow-up post discharge until the end of the study. Patients will be analyzed for safety if they receive at least one dose of the experimental treatment. For efficacy endpoints, analyses will be according to the intent-to-treat principle and outcomes on all enrolled participants will be included for analysis. All power calculations assume Type I error rate of alpha=0.05. Power calculations were done using STATA/SE v16.0.

With a sample size of 40 for a given arm, the expected probability of observing zero or at least one adverse event at varying underlying adverse event rates under a binomial distribution is shown below in Table 3. At this sample size, it is likely to see at least one person with an adverse event even with relatively small rates of adverse reactions. For example, 40 individuals in one arm, there is an 80% chance of observing at least one individual with an event if the underlying AE rate is 4%. The analysis of AE rates will primarily be descriptive due to the lack of power to make formal comparisons with the control arm.

Table 3. Probability of detecting zero individuals or at least one individual with an Adverse Event (AE) for a variety of different underlying AE rates and sample size N =40

AE rate	Pr(0 events)	Pr(1+ event)
0.001	0.96	0.04
0.005	0.82	0.18
0.01	0.67	0.33
0.02	0.45	0.55
0.03	0.30	0.70
0.04	0.20	0.80
0.05	0.13	0.87
0.10	0.01	0.99

While the sample size is driven by safety considerations, we also consider the operating characteristics of the proposed sample size for the analysis of the primary and secondary efficacy endpoints. The primary efficacy outcome is a comparison of the clinical severity score. The severity score is based on

a procedure by Shaw and Fay 2016 [21], which ranks all survivors better than non-survivors, individuals with shorter recovery times as better, individuals with shorter times to death as worse, and non-recovered survivors ranked according to their Day 29 severity score. We considered the power to reject the null hypothesis that there is a 50-50 chance that the individuals receiving the experimental treatment had lower severity compared to the control arm. The analysis of the Win Ratio [22], which simply ranks the experimental participant with a matched control participant as either better or worse by considering the time to death, if evaluable, and otherwise considers the patient ranking according to the time to recovery, or time to Day 29 severity score if not-recovered, and reduces to a simple binomial proportion. For 40 matched experimental-control pairs, we have over 80% power to reject the null proportion= 50% if the experimental treatment is associated with a 80% or higher probability of having better severity than a control participant. The proposed analysis for this endpoint, described in the previous section, is expected to have even better power by also considering the timing of the event and not just the binary outcome of better or worse [21].

One can also consider the power to detect a difference in the secondary survival and recovery time endpoints. Given the sample size of 40 per arm, only very large differences would be detectable with 80% power. For example, we will have about 80% power to detect a difference between arms if the underlying event rate was 0.50 vs 0.80. Power calculations rely on the Pearson's chi-squared test approximation; log-rank statistics provided similar power to detect a hazard ratio of about 0.30.

9.3 Populations for Analyses

- The **safety analysis set** includes all participants who received any amount of the study intervention and for whom post-infusion safety data are available.
- The **per-protocol (PP) analysis set** comprises all participants who completed 1 or 2 unit infusions, have no important protocol deviations, and have valid endpoint data available. These will be documented and tabulated.
- The **intent-to-treat analysis set** includes all participants who were randomized.

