Nonimmune plasma was considered as a placebo, but there may be cross-reactive antibodies in this plasma that would complicate analysis and/or nonspecific immune modulating effects from Fc binding. A half-normal saline with albumin was entertained as a better physical representation of study plasma, but this approach has several shortcomings. First, the albumin will provide oncotic pressure, i.e., it would not be a true inactive placebo. Second, the sequential labeling in the blood bank would be difficult to replicate on this compound, and therefore the labeling would be able to distinguish placebo from active plasma. Therefore, it would still need to be masked. Finally, identification of plasma donor without recent COVID-19 is challenging, given the limited availability of serologic assays to disprove recent infection. Thus, many asymptomatic donors may have recently been infected COVID-19 and their plasma would not serve as a control.

Given the potential for increased risk with a saline control, and the inability to effectively blind the study (discussed below) immune plasma will be compared with standard care (i.e., there is no comparator infusion, saline or other). If a treatment effect is determined to exist, then subsequent studies can dissect the components of the treatment effect (volume load, Fab binding of virus, Fc binding with immune modulation, and oncotic pressure).

This study is not blinded. Saline or other controls would be significantly different in appearance compared to plasma. Plasma needs to be distributed from blood banks. However, hospital blood banks do not have the capabilities of distributing placebo. Conversely, pharmacies could not distribute the study plasma. Hospitals have systems for double-checking administration of blood products, as well as documentation of the administration of blood products in the hospital record (paper or electronic). Mechanisms for documentation of administration of a study drug would not be sufficient for documentation of a blood product, and the mechanisms for documentation of plasma products would not be amenable to documentation of a blinded study product. Therefore, effectively blinding the study, wherein there is high likelihood that the investigative team does not know whether the participant received plasma or saline, was not felt to be practical.

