6 STUDY INTERVENTION

6.1 Study Intervention(s) Administration

6.1.1 *Study Intervention Description*

Participants in the treatment arm will receive standard care plus 2 units of COVID-19 convalescent plasma on Study Day 1. Participants will receive plasma compatible with their blood type (per standard blood bank practice).

6.1.2 *Dosing and Administration*

Participants will be randomized 1:1, stratified on mechanical ventilation and receipt of remdesivir at baseline, to receive either PCCP and standard care (treatment arm) or standard care alone (control arm).

For those participants assigned to the treatment group, the study plasma should be administered as soon as possible. Before administration of study plasma, the investigator must check for appropriate investigational study label on the plasma bag.

The calendar date and 24-hour clock time for study plasma administration should be recorded for the start and end of each infusion. The two infusions should be separated by at least 1 hour after the end of the first and the start of the second infusion in order to assess for any immediate AEs from the first unit. The interval may be extended if clinically indicated. This should be noted on the infusion record and will not be considered a protocol violation.

If an AE considered related to the administration of the investigational product occurs during infusion, the infusion may be slowed temporarily or permanently discontinued, as deemed appropriate by the investigator. As a guide, local side effects (e.g., infusion site burning), nonallergic systemic effects (e.g., chills), and mild allergic reactions (itching, hives) can generally be alleviated by slowing the rate of infusion, whereas serious allergic side effects (e.g., wheezing, hypotension) should result in the cessation of study plasma infusion. The treating investigator is ultimately responsible for making the decision to slow or stop study plasma infusion. If the infusion is discontinued, the participant should be treated according to best available local practices and procedures, and the Principal Investigator should notify the Sponsor Medical Director and HUP Blood Bank. Reason(s) for premature discontinuation of any plasma infusion must be documented in the medical record (source document) and on the CRF.

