6.3 Measures to Minimize Bias: Randomization and Blinding

Individuals will be randomized to the intervention or control arm in a 1:1 ratio. Randomization will occur in a blinded fashion using Redcap. Allocation will be determined using a permuted block algorithm with varying block sizes. We will stratify randomization based on whether or not a patient is on mechanical ventilation and on [remdesivir](#) at baseline. Though the intervention will not be blinded, we will attempt to minimize bias by blinding study personnel, such as individuals running laboratory assays, to the extent that it is possible.

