9.4 Statistical Analyses

9.4.1 General Approach

Descriptive statistics (mean, standard deviation, minimum, median interquartile range, and maximum values for continuous variables; and frequencies and percentages for categorical variables) will be computed for all study variables for the above populations. Unless otherwise specified, a complete case analysis will be considered such that missing values will not be replaced, and calculations will be done on available reported values. If there is a substantial amount of missing data we may consider imputation methods and adjust the analyses accordingly. Analyses will primarily be descriptive; estimates will be presented with 95% confidence intervals. Any significance testing will be done at the 0.05 level. Details for the primary and key secondary analyses are provided below. A formal Statistical Analysis Plan (SAP) will be developed prior to performing analyses of the study endpoints.

9.4.2 *Analysis of the Primary Endpoint(s)*

The primary safety endpoint is cumulative incidence of serious adverse events (SAEs) at Day 29, calculated separately by arm as the percent of individuals who had at least one SAE by Day 29. The SAE rate at all other time points of the study will also be calculated. The overall SAE incidence will be presented, as well as separately by system organ class and preferred term groupings. Percentages will be based on the number of participants who were treated (the safety analysis set). Additional frequencies will be presented with respect to maximum severity and to relationship to COVID19 and study product. Multiple occurrences of the same AE will be counted only once according to the highest occurring grade and relationship to study product/COVID19.

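### The denominator rule for the primary Day 29 SAE percentage admits only plasma recipients, so it cannot be applied to the control arm that must also be reported

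*Combined protocol and SAP*

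**What the plan says.** All references are to the combined protocol and SAP.

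- **Endpoint (9.4.2).** The primary safety endpoint is the Day 29 cumulative incidence of SAEs, "calculated separately by arm as the percent of individuals who had at least one SAE by Day 29".
- **Denominator (9.4.2, same paragraph).** "Percentages will be based on the number of participants who were treated (the safety analysis set").
- **Safety analysis set (9.3).** It "includes all participants who received any amount of the study intervention and for whom post-infusion safety data are available".
- **Sample size section (9.2).** "Patients will be analyzed for safety if they receive at least one dose of the experimental treatment". The same section also says: "The analysis of AE rates will primarily be descriptive due to the lack of power to make formal comparisons with the control arm".
- **What the intervention is (6.1.1).** "Participants in the treatment arm will receive standard care plus 2 units of COVID-19 convalescent plasma on Study Day 1". Section 6.3 separates the two arms in the same way: "Individuals will be randomized to the intervention or control arm in a 1:1 ratio".
- **What controls receive (4.2).** Standard care; "there is no comparator infusion, saline or other".
- **Interval (9.1).** The SAE proportion is to be given by arm with a 95% Clopper-Pearson interval. No analysis set is named.
- **Other sets (9.3).** The intent-to-treat set is everyone randomised; 9.2 and 9.4.2 assign it to efficacy. The per-protocol set requires that one or two unit infusions were completed.

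**The concern.** One paragraph of 9.4.2 asks for a percentage in each of two arms and then sets a denominator that only one arm can supply. The wording is not an isolated slip. Sections 9.2, 9.3 and 9.4.2 state the restriction in three different ways: experimental treatment received, study intervention received with post-infusion data, and participants treated.

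The control figure matters for interpretation. Section 9.1 hypothesises that SAE rates will not differ between arms, and 9.4.4 expects these patients to carry a substantial baseline SAE risk. A plasma-arm percentage with nothing beside it would say little about plasma.

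The repair also involves a choice. If controls were simply added from randomisation while the plasma arm kept its infusion condition, a plasma-arm participant with an SAE between randomisation and infusion would leave the denominator, and a control with the same event at the same time would be counted. In an open-label trial, that choice should be written down before outcomes are reviewed.

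**Working it through.** **Inputs.** 80 participants randomised 1:1 (9.2), so 80 / 2 = 40 per arm. Plasma goes to the treatment arm only (6.1.1). There is no infusion in the control arm (4.2). The safety set requires (a) any study intervention and (b) post-infusion safety data (9.3).

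**The plan's own safety figures (9.2, Table 3).** The probability of at least one participant with an event among 40 is 1 − (1 − p)^40. At p = 0.04 this is 1 − 0.96^40 = 1 − 0.195 = 0.805, against the stated 0.80. All eight rates reproduce:

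| AE rate | Stated | Recomputed |
|---|---|---|
| 0.001 | 0.04 | 0.039 |
| 0.005 | 0.18 | 0.182 |
| 0.01 | 0.33 | 0.331 |
| 0.02 | 0.55 | 0.554 |
| 0.03 | 0.70 | 0.704 |
| 0.04 | 0.80 | 0.805 |
| 0.05 | 0.87 | 0.872 |
| 0.10 | 0.99 | 0.985 |

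Table 3 concerns a single arm of 40, so the denominator problem does not touch it.

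**Applying the 9.3 definition to each arm.**

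| Condition | Plasma arm | Control arm |
|---|---|---|
| Received study intervention | up to 40 | 0 |
| Has post-infusion safety data | up to 40 | 0 |
| Safety set n | up to 40 | 0 |
| SAE percentage, 100·x/n | defined | x/0, undefined |

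The control count of 0 assumes that no control is given plasma in error. The Clopper-Pearson interval for the control arm fails in the same way, but only if 9.1 is read together with 9.4.2, because 9.1 names no set.

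**Could standard care count as study intervention?** That would meet condition (a) but not condition (b), since a control has no infusion to be followed from. Section 9.2 also says experimental treatment, and 6.3 sets intervention against control. This reading does not rescue the rule.

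**Does another passage give controls a denominator for this percentage?** No passage assigns one. Section 9.4.1 calls for descriptive statistics on all study variables in all the listed populations, which include intent-to-treat. Section 9.4.4 calls for by-arm proportions at Days 15, 22, 29 and 60 without naming a set. Both would produce control figures, but neither replaces the specific denominator that 9.4.2 gives the primary endpoint.

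**Per-protocol set.** Its infusion-completion condition also gives control n = 0.

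**The case against.** The strongest case for leaving this alone is that no analyst would be misled. Section 3.2 frames safety as plasma plus standard care against standard care alone, and 9.1, 9.4.2 and 9.4.4 all ask for results by arm. Section 8.4.4 records Grade 3 and 4 AEs and all SAEs from consent through Day 60 with no restriction to plasma recipients, so the control data will exist. The analysis is descriptive, and no test, power figure or sample size depends on the safety set. The formal SAP promised in 9.4.1 is not in the supplied text and may settle the matter.

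Most of this stands, and it limits the severity. A reader might infer that the trial will have no control SAE rate, or that the primary safety comparison is lost. The documents do not support that: the data are collected, the intent is explicit, and 9.4.1 and 9.4.4 yield by-arm figures. Nor is the never-infused plasma-arm participant left in doubt by the current text, which excludes that person.

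What the objection does not remove is the conflict itself. The one sentence that fixes the primary endpoint's denominator cannot be applied to one of the two arms. A later SAP would still have to agree with the protocol or override it openly.

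**Conclusion.** The point holds as a moderate wording error in the rule for a primary endpoint. Under the 9.4.2 denominator, read with 9.2 and 9.3, the safety set has up to 40 plasma participants and 0 controls, so the control percentage is undefined.

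This rests on a literal reading of those three sections, on 40 participants per arm, and on no control receiving plasma in error. The counts of 40 and 0 are the full measure of the defect. The documents give no expected SAE rate, and intervals at assumed counts would only show the ordinary precision of 40 participants. Table 3 and the efficacy analyses are unaffected.

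**What to change.** 1. In 9.1 and 9.4.2, base the by-arm primary SAE percentage and its Clopper-Pearson interval on one named set whose entry rule is the same in both arms. One workable form is all randomised participants with any safety follow-up from randomisation (Study Day 1), analysed by assigned arm, with no infusion condition in either arm. Waiving the condition for controls only would create the unequal entry described above.
2. Align the safety sentence in 9.2, the safety set definition in 9.3 and the reference to treated participants in 9.4.2 with that set.
3. Keep an infused-only set, under its own name, for infusion-specific summaries such as discontinued infusions. If wanted, add a supportive as-treated table, which would show where any never-infused plasma-arm participant or any control given plasma is counted.
4. Give the per-protocol set in 9.3 a criterion that controls can meet.
5. Carry the same definitions into the formal SAP before outcome data are reviewed.

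The cost is wording in 9.1, 9.2, 9.3 and 9.4.2, and at most one extra table. No new participants, visits or data are needed.

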9.4 Statistical Analyses

9.4.1 General Approach

Descriptive statistics (mean, standard deviation, minimum, median interquartile range, and maximum values for continuous variables; and frequencies and percentages for categorical variables) will be computed for all study variables for the above populations. Unless otherwise specified, a complete case analysis will be considered such that missing values will not be replaced, and calculations will be done on available reported values. If there is a substantial amount of missing data we may consider imputation methods and adjust the analyses accordingly. Analyses will primarily be descriptive; estimates will be presented with 95% confidence intervals. Any significance testing will be done at the 0.05 level. Details for the primary and key secondary analyses are provided below. A formal Statistical Analysis Plan (SAP) will be developed prior to performing analyses of the study endpoints.

9.4.2 *Analysis of the Primary Endpoint(s)*

The primary safety endpoint is cumulative incidence of serious adverse events (SAEs) at Day 29, calculated separately by arm as the percent of individuals who had at least one SAE by Day 29. The SAE rate at all other time points of the study will also be calculated. The overall SAE incidence will be presented, as well as separately by system organ class and preferred term groupings. Percentages will be based on the number of participants who were treated (the safety analysis set). Additional frequencies will be presented with respect to maximum severity and to relationship to COVID19 and study product. Multiple occurrences of the same AE will be counted only once according to the highest occurring grade and relationship to study product/COVID19.

The primary efficacy endpoint is the clinical severity score and will be calculated based on all randomized individuals (the intent-to-treat set). The key parameter of interest will be the comparison of clinical severity between individuals receiving the experimental intervention versus control, as measured by a clinical severity score that takes into account the survival time, recovery time, and Day 29 severity score for survivors who had not recovered by Day 29. Recovery is defined by time to reaching levels 1-3 in the 8-point ordinal scale. The severity score for the primary efficacy endpoint is calculated based on a procedure proposed by Shaw and Fay 2016 [21], which ranks all survivors better than non-survivors, individuals with shorter recovery times as better, and individuals with shorter times to death as worse. Shaw and Fay 2016 showed this test statistic can be interpreted as a weighted average of the log-rank type test statistic for survival and the one for time to recovery amongst survivors. If there are participants who survive to Day 29 but have not yet recovered, their clinical severity will be determined by their Day 29 ordinal severity score, using time to reach that level to rank those who had the same Day 29 ordinal severity. It is anticipated that this analysis will have more power to detect differences than looking only at only an individual endpoint. Secondary endpoints will include a comparison of each of the individual endpoints: time to recovery and survival. Further details for the statistical analysis will be provided in the SAP

9.4.3 *Analysis of the Secondary Endpoint(s)*

Key secondary efficacy endpoints include survival and time to recovery and will generally be calculated using the intent-to-treat set. Kaplan-Meier survival curves will be calculated by arm and compared with a Peto-Peto generalized Wilcoxon test. In the event that deaths that occur, the cumulative incidence of recovery will be estimated and compared between groups using Gray's test, which will be able to capture a lower time to recovery due to either a slower event rate or a higher death rate. For interpretive purposes the cause specific hazard ratios for will also be calculated for each event type, survival and recovery, along with the Peto-Peto test. In the event of no deaths, time to recovery will be summarized with the Kaplan-Meier and compared using the Peto-Peto generalized Wilcoxon test.

Cumulative incidence curves will be considered for time-to-event endpoints, treating death as a competing risk. Gray's test, or if the cause-specific hazard ratio was of interest the log-rank test, will be used to compare groups. Binary proportions will be estimated along with Clopper-Pearson 95% confidence intervals and compared between arms using Fisher's exact test. Continuous endpoints will be summarized with means, SD and normal 95% confidence intervals; Wilcoxon rank-sum will be used to compare arms for continuous endpoints. Ordinal endpoints (e.g. 8-point clinical severity score) will be summarized by their multinomial proportions across the different categories at Study Day 15,

22 and 29. An exact Mann-Whitney test will be used to test for whether the ordinal clinical severity was higher in one arm versus the other for ordinal endpoints. Further details for the analysis of secondary endpoints will be provided in the Statistical Analysis Plan.

